9.1.3. Figures

Figure 14.2.1.1.1: Sweat Chloride (mmol/L): Subject profile plots over time

Subject profile plots over time. Each treatment group will be on a separate plot, with all subjects of the same treatment group on the same plot. With horizontal reference lines at 40 and 60 mmol/L. Any unscheduled results will also be part of this plot.

Parameters:

- Sweat Chloride (from arm with greatest volume)
- Sweat Chloride (mean value from both arms)

The figure will show:

- OC in ITT.

Figure 14.2.1.1.2: Sweat Chloride (mmol/L): Subject profile on change from baseline plots over time

Change from baseline subject profile plots over time. Each treatment group will be on a separate plot, with all subjects of the same treatment group on the same plot. With a horizontal reference line at zero, indicating no change., plots will start with a zero mean at baseline. Any unscheduled results will also be part of this plot.

Parameters:

- Sweat Chloride (from arm with greatest volume)
- Sweat Chloride (mean value from both arms)

The figure will show:

- OC in ITT.

Figure 14.2.1.1.3: Sweat Chloride (mmol/L): Mean (+/- SE) plots of the actual values over time

Mean (with SE) plots of the actual values over time. Unscheduled results will not be part of this plot.

Parameters:

- Sweat Chloride (from arm with greatest volume)
- Sweat Chloride (mean value from both arms)

The figure will show:

- LOCF in ITT.
- OC in ITT

Figure 14.2.1.1.4: Sweat Chloride (mmol/L): Mean (+/- SE) plots of the changes from baseline over time

Mean (with SE) plots of the changes from baseline over time. Unscheduled results will not be part of this plot. With a horizontal reference line at zero, indicating no change. Plots will start with a zero mean at baseline.

Parameters:

- Sweat Chloride (from arm with greatest volume)
- Sweat Chloride (mean value from both arms)

The figure will show:

- LOCF in ITT.
- OC in ITT

Figure 14.2.1.1.5: Sweat Chloride (mmol/L): Sub-group analyses: Mean (+/- SE) plots of the changes from baseline over time

Mean (with SE) plots of the changes from baseline over time for each sub-group. Each sub-group category will be done in a separate plot. Unscheduled results will not be part of this plot. With a horizontal reference line at zero, indicating no change. Plots will start with a zero mean at baseline.

Parameters:

- Sweat Chloride (from arm with greatest volume)
- Sweat Chloride (mean value from both arms)

The following sub-groups will be shown:

- By target C_{trough} at Day 15
- By target C_{trough} at Day 29
- By target C_{trough} at Day 15 and 29
- By sweat chloride at baseline
- By %FEV1 at baseline

The figure will show:

- LOCF in ITT.
- OC in ITT

Figure 14.2.1.1.6: Sweat Chloride (mmol/L): Pooled analyses: Mean (+/- SE) plots of the changes from baseline over time

Mean (with SE) plots of the changes from baseline over time on pooled treatment. Each sub-group category will be done in a separate plot. Unscheduled results will not be part of this plot. With a horizontal reference line at zero, indicating no change. Plots will start with a zero mean at baseline.

Parameters:

- Sweat Chloride (from arm with greatest volume)
- Sweat Chloride (mean value from both arms)

The following sub-groups will be also provided in this pooled analysis:

- By target C_{trough} at Day 15
- By target C_{trough} at Day 29
- By target C_{trough} at Day 15 and 29

The table will show:

- LOCF in ITT.
- OC in ITT

Figure 14.2.1.1.7: Sweat Chloride (mmol/L): Mean (+/- SE) plots of the percent changes from baseline over time

Mean (with SE) plots of the percent changes from baseline over time. Unscheduled results will not be part of this plot. With a horizontal reference line at zero, indicating no change. Plots will start with a zero mean at baseline.

Parameters:

- Sweat Chloride (from arm with greatest volume)
- Sweat Chloride (mean value from both arms)

The figure will show:

- LOCF in ITT.
- OC in ITT

Figure 14.2.1.1.8: Sweat Chloride (mmol/L): Boxplots on actual values

Boxplots at each timepoint with all treatment groups in the same figure

Parameters:

- Sweat Chloride (from arm with greatest volume)
- Sweat Chloride (mean value from both arms)

The figure will show:

- LOCF in ITT.
- OC in ITT

Figure 14.2.1.1.9: Sweat Chloride (mmol/L): Boxplots on change from baseline

Boxplots on change from baseline at each timepoint with all treatment groups in the same figure

Parameters:

- Sweat Chloride (from arm with greatest volume)
- Sweat Chloride (mean value from both arms)

The figure will show:

- LOCF in ITT.
- OC in ITT

9.1.4. Listings

Listing 16.2.6.1: Sweat Chloride (mmol/L): Full listing

Listing per subject and per time point of all data related to the sweat chloride: actual values, changes from baseline. A flag “H” and “HH” will be added to values above the upper limit of normal (Values > 60 mmol/L will be flagged as “HH”. Values in [40,60[mmol/L will be flagged as “H”).

The listing will show: OC in ITT population.

9.2. SPIROMETRY

9.2.1. Parameters

During study visits on Days 1, 15 and 29, spirometry must be performed before the morning dose. On Day 1 and Day 29, the spirometry test is to be performed prior to the morning dose of study drug and an additional spirometry must be performed after the study drug intake around 1-2 hours post-dose.

Spirometry can be performed pre-bronchodilator* or post-bronchodilator at screening but should take place prior to bronchodilator use at all other visits. But in practice, if on Day 1, the subject forgets to withhold his/her dose of bronchodilator then all subsequent spirometry should be collected post-bronchodilator, to be consistent with the conditions for the baseline measurement. And if on Day 1 spirometry is collected pre-bronchodilator, but then at a subsequent visit the subject forgets to withhold his/her dose of bronchodilator, then spirometry should be collected post-bronchodilator for that visit only.

* pre-bronchodilator is defined as:

- short-acting more than 4 hours prior to the spirometry assessment
- long-acting bronchodilator at least 12 hours or 24 hours prior to the spirometry assessment

(a spirometry assessment with no use of bronchodilator is equivalent to a pre-bronchodilator assessment)

The values will be used as available via the data transfer from the central laboratory (████████).

Note that at all post-baseline (Day 1) visits:

- Spirometry data taken inconsistently with the baseline will be excluded from the analysis (i.e. if spirometry was performed post-bronchodilator and the one at baseline was performed pre-bronchodilator or if spirometry was performed pre-bronchodilator and the one at baseline was performed post-bronchodilator).
- Spirometry that should be assessed pre-dose and was done post-dose will be excluded from the analysis.
- Spirometry, 1-2h post-dose assessment that was done pre-dose will be excluded from the analysis.

Data with a quality grade of D, E or F will be excluded too.

Quality*	Criteria
A	At least 3 acceptable efforts AND the difference between the best two FEV ₁ and FVC values is equal to or less than 100 ml (80 ml if FVC < 1.0 L)
B	At least 3 acceptable efforts AND the difference between the best two FEV ₁ and FVC values is equal to or less than 150 ml (100 ml if FVC < 1.0 L)
C	At least 2 acceptable efforts AND the difference between the best two FEV ₁ and FVC values is equal to or less than 200 ml (150 ml if FVC < 1.0 L)
D	At least 2 acceptable efforts but the results are not Reproducible
E	At least 1 acceptable effort
F	No acceptable test available

* SQ_QUALGRAD from SDTM.re dataset.

Available parameters:

- FEV₁ (L) and percent predicted FEV₁ for age, gender, and height
- Forced Vital Capacity (FVC) (L) and percent predicted FVC for age, gender, and height
- FEV₁/FVC ratio
- Forced expiratory flow between 25% and 75% of exhaled volume (FEF₂₅₋₇₅)

Analysis will present (to be done on all available parameters unless specified):

- Actual values
- Change from baseline (Day 1 pre-dose):
change at time point t = (time point t value) – (baseline value)
- Percent change from baseline (Day 1 pre-dose):
%change at time point t = 100 x (time point t value – baseline value) / (baseline value)

9.2.2. Tables

Table 14.2.1.2.1: Spirometry: Descriptive statistics of the actual values per time point

Descriptive statistics of actual values per parameter, treatment group and analysis visit.

The table will show:

- LOCF in ITT.
- OC in ITT

Table 14.2.1.2.2: Spirometry: Sub-group analyses: Descriptive statistics of the actual values per time point

Descriptive statistics of the actual values per parameter, treatment group and analysis visit for each sub-group analysis.

The following sub-groups will be shown:

- By target C_{trough} at Day 15
- By target C_{trough} at Day 29
- By target C_{trough} at Day 15 and 29
- By sweat chloride (from arm with greatest volume) at baseline

- By sweat chloride (mean value from both arms) at baseline
- By %FEV1 at baseline

The table will show:

- LOCF in ITT.
- OC in ITT

Table 14.2.1.2.3: Spirometry: Pooled analyses: Descriptive statistics of the actual values per time point

Descriptive statistics of the actual values per parameter on pooled treatment group and analysis visit.

The following sub-groups will be also provided in this pooled analysis:

- By target C_{trough} at Day 15
- By target C_{trough} at Day 29
- By target C_{trough} at Day 15 and 29

The table will show:

- LOCF in ITT.
- OC in ITT

Table 14.2.1.2.4: Spirometry: Descriptive statistics of the changes from baseline per time point

Descriptive statistics of changes from baseline per parameter, treatment group and analysis visit. The actual value at baseline will also be presented in this table.

P-values are generated from an ANCOVA model on the changes from baseline at each time point with treatment as factors and baseline value as covariate. Pairwise comparison (dose group vs placebo) will be provided as well.

P-values will be generated also from a Kruskal-Wallis test (overall treatment effect) and Wilcoxon rank sum test (pairwise comparison with placebo) as sensitivity analysis.

Descriptive statistics will be done on all available parameters, but inferential statistics will be done only on FEV1 and %FEV1.

The table will show:

- LOCF in ITT.
- OC in ITT (only descriptive, no inferential statistics)

Table 14.2.1.2.5: Spirometry: Descriptive statistics of the changes from baseline per time point on Placebo groups

Descriptive statistics of changes from baseline per cohort, analysis visit on placebo (cohort A), on placebo (cohort B), on pooled placebo. The actual value at baseline will also be presented in this table.

The table will show:

- LOCF in ITT.

Table 14.2.1.2.6: Spirometry: Sub-group analyses: Descriptive statistics of the changes from baseline per time point

Descriptive statistics of changes from baseline per parameter, treatment group and analysis visit for each sub-group. The actual value at baseline will also be presented in this table.

The following sub-groups will be shown:

- By target C_{trough} at Day 15
- By target C_{trough} at Day 29
- By target C_{trough} at Day 15 and 29
- By sweat chloride (from arm with greatest volume) at baseline
- By sweat chloride (mean value from both arms) at baseline
- By %FEV1 at baseline

The table will show:

- LOCF in ITT.
- OC in ITT

Table 14.2.1.2.7: Spirometry: Pooled analyses: Descriptive statistics of the changes from baseline per time point

Descriptive statistics of changes from baseline per parameter, per pooled treatment group and analysis visit. The actual value at baseline will also be presented in this table.

The following sub-groups will be also provided in this pooled analysis:

- By target C_{trough} at Day 15
- By target C_{trough} at Day 29
- By target C_{trough} at Day 15 and 29

The table will show:

- LOCF in ITT.
- OC in ITT

Table 14.2.1.2.8: Spirometry: Descriptive statistics of the percent changes from baseline per time point

Descriptive statistics of percent changes from baseline per parameter, treatment group and analysis visit. The actual value at baseline will also be presented in this table.

The table will show:

- LOCF in ITT.
- OC in ITT

Table 14.2.1.2.9: Spirometry: Sensitivity analyses on the changes from baseline values

Additional sensitivity analysis will be explored by using Mixed Effects Model for Repeated Measures (MMRM). The model will include treatment and analysis visit as fixed effects and baseline as a covariate, treatment*analysis visit as interaction terms and subject as random effect. Pairwise comparisons will be presented.

This table will be done only on FEV1 and %FEV1.

The table will show:

- OC in ITT.

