7.1.3. Analyses of Efficacy Parameters

Descriptive statistics of actual values, changes from baseline (pre-dose on Day 1), and percent changes from baseline will be provided.

An analysis of covariance (ANCOVA) model on the changes from baseline at each time point, with treatment as factor and baseline value as covariate, will be applied to the following parameters:

- Sweat chloride concentration;
- FEV₁;
- CFQ-R scores.

Between-group comparisons will be done for each GLPG2222 group versus the pooled placebo group (if the study is performed in both Cohorts A and B) or versus placebo in Cohort A (if the study is only performed in Cohort A).

Missing data will be imputed, also for subjects who prematurely discontinue the study. The primary imputation method will be the last-observation-carried-forward. An observed-case analysis will also be performed.

A sensitivity analysis will be performed by using non-parametric tests. The GLPG2222 groups and pooled placebo group (if the study is performed in both Cohorts A and B) or the GLPG2222 groups and placebo in Cohort A (if the study is only performed in Cohort A) will be compared using a Kruskal-Wallis test (overall treatment effect) and Wilcoxon rank sum tests (pairwise comparisons versus the corresponding placebo group).

Additional exploratory analyses and graphical presentations have been described in this SAP to better understand the data.

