Descriptive statistics of changes from baseline per cohort, analysis visit on placebo (cohort A), on placebo (cohort B), on pooled placebo. The actual value at baseline will also be presented in this table.

The table will show:

- LOCF in ITT.
- OC in ITT

Table 14.2.1.3.6: CFQ-R: Sub-group analyses: Descriptive statistics of the changes from baseline per time point

Descriptive statistics of changes from baseline, treatment group and analysis visit for each sub-group analysis will be done only for CFQ-R respiratory domain score. The actual value at baseline will also be presented in this table.

The following sub-groups will be shown:

- By target C_{trough} at Day 15
- By target C_{trough} at Day 29
- By target C_{trough} at Day 15 and 29
- By sweat chloride (from arm with greatest volume) at baseline
- By sweat chloride (mean value from both arms) at baseline
- By %FEV1 at baseline

The table will show:

- LOCF in ITT.
- OC in ITT

Table 14.2.1.3.7: CFQ-R: Pooled analyses: Descriptive statistics of the changes from baseline per time point

Descriptive statistics of changes from baseline per pooled treatment group and analysis visit will be done only for CFQ-R respiratory domain score. The actual value at baseline will also be presented in this table.

The following sub-groups will be also provided in this pooled analysis:

- By target C_{trough} at Day 15
- By target C_{trough} at Day 29
- By target C_{trough} at Day 15 and 29

The table will show:

- LOCF in ITT.
- OC in ITT

Table 14.2.1.3.8: CFQ-R: Descriptive statistics of the percent changes from baseline per time point

Descriptive statistics of percent changes from baseline per treatment group and analysis visit for each score. The actual value at baseline will also be presented in this table.

The table will show:

- LOCF in ITT.
- OC in ITT

Table 14.2.1.3.9: CFQ-R: Sensitivity analyses on the changes from baseline values

Additional sensitivity analysis will be explored by using Mixed Effects Model for Repeated Measures (MMRM). The model will include treatment and analysis visit as fixed effects and baseline as a covariate, treatment*analysis visit as interaction terms and subject as random effect for each score. Pairwise comparisons will be presented.

The table will show:

- OC in ITT.

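### The exploratory MMRM, read as written, assumes one variance for all visits; if variances differ its per-visit standard errors are off, most plausibly for FEV1

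*SAP*

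**What the plan says.** Four SAP tables specify the same additional, exploratory mixed model on observed cases: 14.2.1.1.11 (sweat chloride, section 9.1.2), 14.2.1.2.9 (spirometry, 9.2.2), 14.2.1.3.9 (CFQ-R, 9.3.2) and 14.2.3.9 (biomarkers, 11.2). Each has treatment, visit and baseline, and then "treatment*analysis visit as interaction terms and subject as random effect". No residual covariance structure, degrees-of-freedom method, fallback or list of visits is given. For spirometry, "This table will be done only on FEV1 and %FEV1".

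The main inference is different. SAP 7.1.3 plans "An analysis of covariance (ANCOVA) model on the changes from baseline at each time point", so each time point has its own residual variance. For missing data, "The primary imputation method will be the last-observation-carried-forward". In the ANCOVA tables the observed-case rows are limited to "OC in ITT (only descriptive, no inferential statistics").

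Spirometry is taken pre-dose at every visit. On Day 1 and Day 29, "an additional spirometry must be performed after the study drug intake around 1-2 hours post-dose" (SAP 9.2.1). The follow-up visit is two weeks after the last dose.

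**The concern.** A random subject intercept with independent residuals is compound symmetry: one total variance for all visits and one correlation for all pairs. FEV1 could contribute up to five changes from baseline: Day 1 post-dose, Day 15, Day 29 pre-dose, Day 29 post-dose and follow-up off drug. It is doubtful that a change over one or two hours varies as much as a change over four weeks. If it varies less, the pooled variance is too low for Day 29 and too high for Day 1 post-dose.

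At stake is how the missing-data check is read. Table 14.2.1.2.9 and its counterparts hold the only observed-case tests, and SAP 5.4.2 lets LOCF carry forward even a baseline value. If the mixed model and the LOCF ANCOVA disagree, a reader could not tell an effect of missing data from an effect of pooling variances.

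**Working it through.** **The plan's own figure.** The documents state no figure for the mixed model. The sample size (Protocol 7.1: SD 10 mmol/L, difference 14 mmol/L, two-sided 5%, 80% power) does reproduce. A two-sample t test has 79.6% power with 9 per group and 84.1% with 10, so 10 per group and 5 × 10 = 50. For Cohort A alone, 5 versus 10 at 16 mmol/L gives 79.7% with pooled error df of 22. Here this only fixes the group size at 10, with the placebo groups pooled.

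**Formula.** With complete data and n per group, the random-intercept REML total variance is the mean of the per-visit variances:

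- model SE at visit t = sqrt(mean variance × 2/n)
- true SE at visit t = sqrt(variance at t × 2/n)
- ratio = sqrt(mean variance / variance at t)

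Correlations do not appear. With complete data, only unequal variances distort the per-visit standard errors.

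**Inputs.** The only SD in the documents is the 10 mmol/L for sweat chloride change. All per-visit SDs below are assumptions (FEV1 in percentage points).

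**Worked example.** FEV1 SDs 3/6/7/7/7 for the five time points:

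- mean variance = (9 + 36 + 49 + 49 + 49)/5 = 38.4
- Day 29: sqrt(38.4/49) = 0.885. With a cut-off of 2.0, the rejection rate is about P(|Z| > 2.0 × 0.885) = P(|Z| > 1.77) = 7.7%; simulation gave 7-8%.
- Day 1 post-dose: sqrt(38.4/9) = 2.07

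**Dependence on one ratio.** Let the Day 1 post-dose SD be a fraction f of a common SD at the other four time points. The mean variance is then (f² + 4)/5 in units of the common variance.

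- f = 0.5: 0.85, so 0.92 at the other four and 1.84 at Day 1 post-dose
- f = 0.75: 0.9125, so 0.96 and 1.27
- f = 1: no error

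**Four other sets of assumed SDs** (ratio from the formula; rejection rate from 10,000 simulated trials each, 5 groups of 10, no baseline covariate):

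| SDs: Day 1 post / Day 15 / Day 29 pre / Day 29 post / follow-up | Ratio, Day 1 post | Ratio, Day 15 | Ratio, Day 29 pre | Ratio, follow-up | Rejection, Day 29 pre | Rejection, follow-up |
|---|---|---|---|---|---|---|
| 2.17 / 5.35 / 5.88 / 5.88 / 6.00 | 2.43 | 0.984 | 0.895 | 0.877 | 7.7% | 8.3% |
| 3.55 / 5.35 / 6.05 / 6.05 / 6.37 | 1.57 | 1.041 | 0.920 | 0.874 | 6.6% | 8.1% |
| 1.56 / 6.73 / 7.15 / 7.15 / 7.20 | 4.08 | 0.944 | 0.889 | 0.882 | 7.7% | 7.9% |
| 4.26 / 5.62 / 5.91 / 5.91 / 5.98 | 1.31 | 0.992 | 0.943 | 0.932 | 6.1% | 6.8% |

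The Day 1 post-dose test rejected in 0% to 1.0%. A separate variance per visit gave 4.6%-5.3% throughout.

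**Check with fitted models.** 300 random-intercept fits with the baseline covariate (SDs 2.2 to 6.0) gave ratios of 2.23, 0.94, 0.91, 0.89 and 0.85, in the order of the five time points. Rejection rates were 0%, 5%, 8%, 9% and 10%. With 300 fits, an 8% rate has a Monte Carlo standard error of sqrt(0.08 × 0.92/300) = 1.6 points.

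**Without the post-dose tests.** Using Day 15, Day 29 and follow-up from the four sets above, ratios were 0.93-1.11 and rejection 2.9%-6.2% (5.1%-5.3% at Day 29). SDs of 6/7/7 give sqrt(44.67/49) = 0.955 at Day 29 and 5.6%-6.0%. A steeper 6/8/7 gives sqrt(49.67/64) = 0.881 and about 7.9%.

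**Sweat chloride (three visits).** The result depends on the assumed pattern. SDs of 9/10/7 give 8.2% at Day 29, 9/10/10 give 5.5%-5.6%, and 9/10/11 give 4.4%-4.8%. SDs of 8/10/12 give 4.4% at Day 29 but 9.2% at follow-up.

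**The case against.** The strongest reply is that nothing in the documents shows unequal variances, and that this is an additional, exploratory analysis with no decision rule attached, in a study that makes no multiplicity adjustment. Both points stand, so the conclusion has to be conditional and modest.

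The SAP also does not say that post-dose FEV1 enters the model. The time-window table in SAP 4.3 ties its Day 1 post-dose label to vital signs and has no Day 29 post-dose label. On the other side, SAP 5.4.2 gives post-dose spirometry its own LOCF rule. SAP 9.2.1 drops a post-dose test only when it was actually done pre-dose, whereas sweat chloride and CFQ-R each carry a pre-dose filter that spirometry lacks. Inclusion is likely but not settled.

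MMRM is often shorthand for an unstructured residual matrix, so the wording may be loose rather than a choice. In that case the text still needs correcting, because it specifies something else.

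A reader might infer that the trial would miss an acute FEV1 fall after dosing. The documents do not support this. If the post-dose tests are analysis visits, the ANCOVA in Table 14.2.1.2.4 already tests them with their own variance. If they are not, the large Day 1 distortion does not arise. A reader might also blame the high correlation between two tests on the same morning; with complete data it leaves per-visit standard errors unchanged.

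Finally, the calculations assume complete data, whereas the model's purpose is to handle missing data. That limitation stands: behaviour under dropout was not quantified.

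**Conclusion.** The point holds conditionally. As written, the four models assume equal variance at every visit. If that fails, per-visit standard errors err in both directions. For FEV1 with the post-dose tests included and a less variable Day 1 post-dose change, the Day 29 standard error is about 0.89-0.94 of its true value (type I error about 6-8%), and the Day 1 post-dose standard error is about 1.3-4 times too large. With equal variances the error is nil. With pre-dose visits and follow-up only it is generally small, about 3-11% of the standard error under most of the assumed SDs, and larger only for steeper patterns.

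The stronger reading, that these standard errors are wrong as a matter of fact, needs per-visit SDs that the documents do not give. A general false-positive problem for sweat chloride is not supported either, since the 8.2% needs an assumed fall in variability at follow-up.

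The main ANCOVA is untouched. The point matters because this is the only observed-case inference, and so the only inferential check on LOCF.

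**What to change.** In all four tables, replace the random subject effect with an unstructured within-subject covariance over visits, Kenward-Roger degrees of freedom and a baseline-by-visit term. Name heterogeneous compound symmetry as the fallback if the model does not converge. With complete data this essentially matches the per-time-point ANCOVA, so a disagreement between the two points to missing data. No harm from a single baseline slope was quantified; the interaction is included for that match.

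List the visits in each model. For FEV1 and percent predicted FEV1, use pre-dose Day 15 and Day 29, plus follow-up if wanted. State that post-dose spirometry is tested in the per-time-point ANCOVA.

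The cost is SAP wording and a few lines of code. The downside is more covariance parameters: 3 × 4/2 = 6 for three visits instead of 2, estimated from about 50 subjects.
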